1.4.2 Primary Effectiveness Endpoint

The Primary Effectiveness Endpoint is the rate of successful pulmonary vein electrical isolation with confirmation of entrance and exit block achieved with the Cardiac Cryoablation System (Acute procedural success).

Acute procedural success is defined as the documentation of pulmonary vein isolation following the last cryo application for each of the targeted veins. Demonstration of electrical isolation in ≥ 3 PVs or their anomalous equivalents at the end of the first protocol-defined cryoablation procedure. Documentation will be completed with the Cryterion Circular Mapping Catheter to confirm PVI. The physician should confirm and document entrance and exit block by standard of-care pacing maneuvers during the index procedure.

1.4.3 Additional Effectiveness Endpoint: 12 Month Treatment Success

Treatment success is defined as the proportion of subjects free from symptomatic atrial arrhythmias at 12 months. A treatment failure is defined as a subject being an acute procedural failure, having more than one repeat procedure during the 90-day blanking period or having a documented, symptomatic episode(s) of atrial fibrillation or atrial tachycardia, between 91 and 365 days post index procedure (windows allowed per protocol as shown in Table 2 included). Occurrence or recurrence of a right atrial arrhythmia is not considered a treatment failure post the 90-day blanking period.

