3.5 Additional Effectiveness Endpoint

The additional effectiveness endpoint is 12 month treatment success, defined as the proportion of subjects free from symptomatic atrial arrhythmias at 12 months.

The rate of 12 month success will be presented as a binomial rate (N events/ N subjects) with corresponding exact binomial 95% confidence interval. The rates will be compared to the 12 month success rates derived from available literature data.

The additional effectiveness endpoint will be assessed in all enrolled subjects who undertake the ablation procedure to the point that the Cryoablation Balloon is used to deliver at least one cryo application (Treated subjects). Subjects who withdraw from the study prior to their 12 month visit without experiencing an event will be considered ineligible for this analysis.

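### Twelve-month treatment success is scored without regard to antiarrhythmic drug use, so its comparison with literature rates is like for like only where those rates also ignore drug use

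*SAP*

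**What the plan says.** SAP section 1.4.3 defines the endpoint from both sides. On success: "Treatment success is defined as the proportion of subjects free from symptomatic atrial arrhythmias at 12 months". On failure there are three routes. The first two are in one clause: "A treatment failure is defined as a subject being an acute procedural failure, having more than one repeat procedure during the 90-day blanking period". The third is "having a documented, symptomatic episode(s) of atrial fibrillation or atrial tachycardia, between 91 and 365 days post index procedure". One exception follows: "Occurrence or recurrence of a right atrial arrhythmia is not considered a treatment failure post the 90-day blanking period". In this section the SAP refers to the protocol only for the visit windows.

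Section 3.5 repeats the definition: "The additional effectiveness endpoint is 12 month treatment success, defined as the proportion of subjects free from symptomatic atrial arrhythmias at 12 months". It then gives the estimator, "The rate of 12 month success will be presented as a binomial rate (N events/ N subjects) with corresponding exact binomial 95% confidence interval", and the comparison, "The rates will be compared to the 12 month success rates derived from available literature data". The population is Treated subjects, with one exclusion: "Subjects who withdraw from the study prior to their 12 month visit without experiencing an event will be considered ineligible for this analysis".

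No section of the SAP mentions antiarrhythmic drugs, whether as a failure criterion, an intercurrent event, a subgroup or a sensitivity analysis.

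**The concern.** Antiarrhythmic drugs act on the event that defines failure. A subject can be free of documented symptomatic AF or AT after day 90 because the ablation worked, because a drug suppresses the episodes, or both. The SAP's rule gives all of these the same score and reports one number.

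The study has no concurrent arm in which drug use would be shared. The only context for the rate is the literature comparison in section 3.5, and the SAP does not say whether the literature rates are defined on drug, off drug or irrespective of drug, or how definitions will be matched. Without drug status beside the rate, a reader cannot tell whether the two figures measure the same thing. If the definitions are chosen after the data are seen, the choice may also be influenced by the result.

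**Working it through.** **No stated figure to reproduce.** The sample size section is redacted, and the visible text gives no expected success rate, performance goal or drug-use figure for this endpoint. The check is therefore a reading of the scoring rule, followed by a labelled illustration of size.

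**Step 1: apply the rule to the case at issue.** Take a treated subject with acute isolation and at most one repeat procedure in blanking, whose antiarrhythmic drug is started or increased after day 90 and suppresses symptomatic AF/AT that would otherwise have occurred.

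| Failure route in section 1.4.3 | Met? |
|---|---|
| Acute procedural failure | No |
| More than one repeat procedure in the 90-day blanking period | No |
| Documented symptomatic AF/AT, days 91 to 365 | No |

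No route is met, so the subject is a success. The same holds for a subject who stays on a drug throughout and is event-free because of it. Section 3.5 adds nothing that changes either score.

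**Step 2: direction of the comparison.**

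- Literature rate defined off drug: the study rate includes drug-supported successes that the literature rate excludes, so the comparison favours the device.
- Literature rate that ignores drug use: both rates include such subjects, and the comparison is like for like on this point.

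The SAP does not say which case applies.

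**Step 3: size, as an illustration.** Let n be the number analysed, s the number event-free and d the number of those on an antiarrhythmic drug after blanking. The stated rate is s/n and the off-drug rate is (s − d)/n. The difference is d/n, or 1 percentage point per subject when n = 100.

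The value n = 100 is the planned enrolment in SAP section 1.1. The analysed number will be lower if subjects are not treated or withdraw event-free, and each subject then moves the rate by 100/n points, slightly more than 1. The values of s and d are assumptions.

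Exact (Clopper-Pearson) 95% intervals:

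| Assumed s | Assumed d | Off-drug rate | Exact 95% CI |
|---|---|---|---|
| 75 | 0 | 75/100 = 75% | 65.3 to 83.1 |
| 75 | 5 | 70/100 = 70% | 60.0 to 78.8 |
| 75 | 15 | 60/100 = 60% | 49.7 to 69.7 |
| 80 | 0 | 80/100 = 80% | 70.8 to 87.3 |
| 80 | 4 (5% of 80) | 76/100 = 76% | 66.4 to 84.0 |
| 80 | 16 (20% of 80) | 64/100 = 64% | 53.8 to 73.4 |

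**Step 4: what d/n measures.** It removes every event-free subject on a drug. Some of them would have been event-free without it. So d/n is an upper bound on the success created by drugs, not an estimate of bias. Counting only subjects with a new or increased drug removes a subset of the same people, so that rate lies between the off-drug rate and the stated rate.

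**The case against.** The strongest reply is that this is a choice of estimand, not an error. Freedom from symptomatic arrhythmia whatever drugs are taken is a coherent outcome, and sections 1.4.3 and 3.5 agree on it. The SAP nowhere claims that the rate is drug-free. This stands, and it is why the stated rate should be kept. What remains is that the SAP does not label the rate as irrespective of drug use and does not match the comparator to it.

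A second reply is that the protocol, which is not shown, may restrict these drugs after blanking or carry a drug rule for the endpoint. That is possible, and the affected subjects may then be few. But the SAP writes out the scoring rule itself, and a programmer who followed it would produce a rate blind to drug use.

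Third, the endpoint is additional and descriptive, with no performance goal or test in the visible text. That also stands: no error rate, power figure or primary conclusion is affected.

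Two stronger readings are tempting, and the document supports neither. A reader might infer that the reported rate is biased in the device's favour whatever the comparator. It is not: the direction depends on each literature rate's own drug rule, which the SAP does not give. A reader might also cite a subject with asymptomatic or undocumented recurrence who is then given a drug. That subject is a success with or without the drug, because failure requires an episode that is both documented and symptomatic, so the case says nothing about drug use. Only symptomatic episodes that a drug prevents bear on the point.

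**Conclusion.** The point holds in a limited form. As written, the 12-month rate combines subjects who are event-free without antiarrhythmic drugs and subjects who are event-free on them, and it is set against literature rates with no statement of how their drug rules compare. The comparison favours the device where the literature rate is off drug and is unaffected where that rate ignores drug use.

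The true size is unknown. On the assumption of 100 analysed subjects, 75 event-free and 5 to 15 of those on a drug after blanking, the stated and off-drug rates differ by 5 to 15 points. That range is assumed, and each value in it is an upper bound on drug-created success. The change is worth making before the analysis because it is cheap and makes the literature comparison interpretable. It does not undermine the study's primary endpoints.

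**What to change.** In SAP section 3.5:

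1. Keep the stated rate and label it as irrespective of antiarrhythmic drug use.
2. Beside it, in the same denominator and with the same exact 95% interval, report (a) success without antiarrhythmic drug use after the blanking period, and (b) success with a new or increased antiarrhythmic drug after blanking scored as failure. Use the study's own definition of these drugs and its recorded medication data.
3. For each literature rate, state its drug rule and set against it the version that matches.

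This changes scoring and reporting only; nothing in drug management is altered or proposed. The cost is SAP wording, two more rates, and supplementary figures that can only equal or fall below the stated one. It assumes that medication use, including starts and increases after blanking, is recorded in the study database. If it is not, item 1 and the statement of each literature rate's drug rule can still be made, with the limitation reported.

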1.3 Follow-up

Visits include Screening & Baseline, Index Procedure, Discharge, 1 Month, 3 Months, 6 Months and 12 Months and additional follow-up visits (including potential repeat procedures).

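### A left atrial repeat ablation on days 91–365 is not in itself a treatment failure, so a residual group of re-ablated subjects can count as 12-month successes

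*SAP*

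**What the plan says.** SAP section 1.4.3 describes the endpoint positively: "Treatment success is defined as the proportion of subjects free from symptomatic atrial arrhythmias at 12 months". It then lists three ways to fail:

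1. "A treatment failure is defined as a subject being an acute procedural failure";
2. "having more than one repeat procedure during the 90-day blanking period";
3. "having a documented, symptomatic episode(s) of atrial fibrillation or atrial tachycardia, between 91 and 365 days post index procedure", with protocol visit windows allowed.

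One exemption follows: "Occurrence or recurrence of a right atrial arrhythmia is not considered a treatment failure post the 90-day blanking period".

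Section 1.3 expects repeat procedures among the additional follow-up visits, and it does not confine them to the blanking period. Section 3.5 gives the analysis: "The rate of 12 month success will be presented as a binomial rate (N events/ N subjects) with corresponding exact binomial 95% confidence interval". The rate is to be compared with literature rates. The denominator is Treated subjects, less those who withdraw before the 12-month visit without an event. Section 3.5 adds no rule for repeat procedures.

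**The concern.** A repeat procedure bears on failure only in the second route, and that route stops at day 90. During the period in which the endpoint is evaluated, a repeat left atrial ablation has no effect on a subject's classification. What decides it is whether an episode that was both documented and symptomatic also falls on days 91–365.

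A second left atrial ablation for AF/AT in that period is reasonable evidence that the first treatment did not hold. If no qualifying episode is on record, the subject is nevertheless a success. The study is single-arm and the rate will be set against literature rates, so its meaning depends on what counts as failure. Compared with a rule that counts late repeats, the present rule can only give an equal or higher rate.

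**Working it through.** **Step 1: follow a late repeat through the rule.** Take a Treated subject with acute success, at most one repeat in blanking, and a left atrial repeat ablation for AF/AT after day 90.

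| Situation | Route 1 (acute failure) | Route 2 (more than one repeat in blanking) | Route 3 (documented, symptomatic AF/AT, days 91–365) | Result under the SAP |
|---|---|---|---|---|
| Documented symptomatic AF/AT after day 90, then repeat | no | no | yes | failure |
| Recurrence documented only in blanking, repeat after day 90 | no | no | no | success |
| Symptoms without a documented episode, then repeat | no | no | no | success |
| Asymptomatic documented AF/AT, then repeat | no | no | no | success |

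The last three rows assume that no qualifying episode occurs later in the window either. The gap is confined to those rows.

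**Step 2: withdrawal.** Section 3.5 drops subjects who withdraw before 12 months without an event. If event means a failure under section 1.4.3, a subject in one of the last three rows who then withdraws leaves the denominator instead of counting as a failure.

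**Step 3: size.** The SAP gives no expected or target rate for this endpoint, so there is no figure to reproduce. Inputs:

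- N = 100, from the enrolment number in section 1.1. The evaluable number may be lower after withdrawals, so N = 90 is also shown as an assumption.
- Success rate under the SAP rule: assumed 80%, with 70% as an alternative.
- k, the affected subjects who complete follow-up: assumed 0 to 5.
- Interval: exact binomial (Clopper-Pearson), as section 3.5 specifies. For x successes, the lower limit is the 0.025 quantile of Beta(x, N − x + 1) and the upper limit is the 0.975 quantile of Beta(x + 1, N − x).

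With x successes under the SAP rule, the rate when late repeats count as failures is (x − k)/N, so the difference is k/N. At N = 100 that is 1/100, or one percentage point per subject.

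| N | x | k | Rate with late repeats as failures | Exact 95% CI |
|---|---|---|---|---|
| 100 | 80 | 0 | 80.0% | 70.8–87.3 |
| 100 | 80 | 1 | 79.0% | 69.7–86.5 |
| 100 | 80 | 3 | 77.0% | 67.5–84.8 |
| 100 | 80 | 5 | 75.0% | 65.3–83.1 |
| 100 | 70 | 0 | 70.0% | 60.0–78.8 |
| 100 | 70 | 5 | 65.0% | 54.8–74.3 |
| 90 | 72 | 0 | 80.0% | 70.2–87.7 |
| 90 | 72 | 5 | 74.4% | 64.2–83.1 |

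For the withdrawal path, suppose 80 of 100 evaluable subjects succeed and one further re-ablated subject has been dropped. Counting that subject as a failure gives 80/101 = 79.2%, a difference of 0.8 points.

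**The case against.** The rule has a coherent structure. Recurrences in blanking do not count, so a cap on repeats is the only recurrence-related way to fail there. From day 91 the recurrence itself is the failure, which makes a repeat-procedure route largely redundant. This stands, and it rules out several stronger readings.

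- A reader might infer that every subject re-ablated after day 90 is a success. The text does not support that: a documented symptomatic episode on days 91–365 already makes the subject a failure.
- A reader might infer that the rule contradicts itself, because two repeats by day 80 fail and one on day 120 does not. That sets two repeats against one. A single repeat by day 80 is not a failure either. The true asymmetry is narrower: there is a cap on repeats in blanking and none afterwards.
- A reader might object that the outcome after a late repeat reflects two procedures. The same holds for the one repeat allowed in blanking, so the argument does not single out late repeats.
- The asymptomatic case is partly a choice of endpoint, since the SAP defines success by symptomatic arrhythmia. The case documented only in blanking and the case of undocumented symptoms do not depend on that choice.
- A reader might infer that the literature comparison is biased in the study's favour. That depends on how the literature rates treat late repeats, and the SAP does not say.

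It is also fair that this is an additional endpoint, analysed descriptively and with no stated threshold. Section 1.4.3 sits in a protocol summary, and the protocol is not at hand and could contain a further rule. However, the definition reads as complete. Its one reference to the protocol concerns visit windows.

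**Conclusion.** The point holds in limited form. As written, a left atrial repeat ablation on days 91–365 is not a failure in itself. A subject without a documented symptomatic AF/AT episode in that window can therefore be counted as a success, or drop out of the denominator on withdrawal. Relative to a rule that counts late repeats, the effect can only be upward.

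Its size cannot be known from the SAP. It is k/N, and k may be zero. On the assumed range of 0 to 5 subjects at N = 100 it is 0 to 5 percentage points. At the upper end the interval for the changed rate overlaps heavily with the interval under the present rule. That most late repeats already fail through the third route is a reasonable expectation, not a figure from the document. No stated decision rests on this rate, so this is a cheap improvement to an additional endpoint and does not affect the primary analyses.

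**What to change.** In sections 1.4.3 and 3.5, add that any repeat left atrial ablation for AF or AT on days 91–365 after the index procedure is a treatment failure, dated at that procedure. Keep the right atrial exemption and the allowance of one repeat in blanking. State in section 3.5 that such a repeat is an event for the withdrawal rule, so the subject stays in the denominator.

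Report how many subjects fail by this route alone, and show the rate and exact interval under the present definition beside the changed one.

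The cost is about a sentence in each section and one extra table row. Repeat procedures are already expected in follow-up. The reported rate may be slightly less favourable. The wording must agree with the protocol's endpoint definition, so check the protocol first and change both documents together if it has no such rule.

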1.4.4 Secondary Endpoints

Secondary Endpoint Measurements will include:

- All Procedure and device related adverse events*
- Documentation of all targeted PVs that demonstrate isolation immediately post ablation and then show reconnection during entrance/exit block testing
- Recording of time to demonstration of PVI using the Circular Mapping catheter following the initiation of a freeze cycle
- Operator's assessment of handling characteristics with a System Performance Questionnaire**

* be accessed directly from the clinical database (eCRFs hosted on IBM Clinical platform)

** The System Performance Questionnaire is included in the study clinical database and includes questions to the operator to assess quality characteristics of the products, alone and compared to commercially available cryoballoon ablation technologies and circular mapping catheters. The system performance questionnaire will be used with all new clinical users for the first five (5) cases performed with the Cryterion System. After the first 5 cases, users can use the questionnaire to provide specific product feedback related to user experience(s) on an as needed basis (for example: the ability of the cryoablation system to deal with tortuous anatomy of the LA/PVs). In case the investigator reports quality issues in the questionnaire, he should consider if needed, to enter a device deficiency

2 SUBJECT CLASSIFICATION DEFINITIONS

For the purposes of this clinical study, the following definitions regarding the status of a subject will apply:

Enrolled Subject - Any subject who has signed an informed consent form (ICF)

Consent Ineligible Subject – Any subject who has signed the informed consent but is found not to meet all the inclusion/exclusion criteria. This includes a subject who has signed an informed consent form but may be excluded based on the results of the pre-procedure TEE or intracardiac echocardiogram (ICE) evaluation of the left atrial appendage (LAA) and/or PV anatomy. In the event these subjects completed a trans-septal puncture, they will be followed through discharge for the recording of any procedure related adverse events. These subjects will not count towards the enrollment ceiling and will not be considered for the primary endpoints analysis.

Intent Subject – Any subject who has signed an informed consent form (ICF) and is deemed study eligible by meeting all the inclusion and none of the exclusion criteria but does not undergo the ablation procedure. This subject will be withdrawn from the study. Data will be collected up to the point of withdrawal, will not count towards the enrollment ceiling and will not be considered for primary endpoints analysis.

Attempt Subject - Any subject who has signed an informed consent form (ICF) and is deemed study eligible by meeting all the inclusion and none of the exclusion/criteria and undergoes the ablation procedure with any of the investigational device entered in the subjects' body but no energy is delivered to the PVs. This subject will be followed through the 30 days follow up then withdrawn from the study. Data will be collected up to the point of withdrawal, will not count towards the enrollment ceiling and will not be considered for primary endpoints analysis.

Treated Subject – Any screened subject who completes the ablation procedure to the point that any of the investigational products are introduced into the body and Cryo-energy is delivered. Enrolled subjects will be followed for all study outcome measures for the full duration of the clinical study.

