1.2 Study devices

The Cryterion Cardiac Cryoablation System is designed to thermally ablate cardiac tissue in the management of atrial fibrillation. The components and accessories for the system are listed below:

- Cryoablation Balloon Catheter
- Cryo-Console
- Circular Mapping Catheter
- Steerable Sheath, 12 F
- Diaphragm Movement Sensor
- Esophageal Temperature Sensor Cable
- Inter Connection Box
- Cryo-Console Foot Switch

- Cryo-Cable
- Cryo-Catheter Extension Cable
- EP Electrical Cable

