3.3 Primary Safety Endpoint

The primary safety endpoint outcome is freedom from a composite MAE list, outlined in Section 2.4.1 above, and all other serious or non-serious adverse device effects (SADEs or ADEs).

The rate of MAEs and rate of SADEs and ADEs will each be presented separately as well as an overall combined rate of all events. Rates will be presented as the binomial rate (N events/ N subjects) with corresponding exact binomial 95% confidence interval. These rates will be compared to the safety outcome rates derived from available literature data.

Additionally, all adverse events will be summarized by type of event, severity, relationship to the device and/or procedure, and timing of event relative to the procedure date. Listings of all adverse events and separate listings of events meeting the safety endpoint will be provided.

The primary safety endpoint will be assessed in all enrolled subjects who undertake the ablation procedure to the point that the Cryoablation Balloon is inserted into the subject (Attempt and Treated subjects).

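### The primary safety population is defined inconsistently and not by exposure, so some procedure-related MAEs can fall outside the primary MAE rate

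*SAP*

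**What the plan says.** Section 2 sorts consented subjects into classes.

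- **Consent Ineligible.** Signed consent but fails the criteria. The finding may come late: a subject "may be excluded based on the results of the pre-procedure TEE or intracardiac echocardiogram (ICE) evaluation". Where a trans-septal puncture has been completed, "they will be followed through discharge for the recording of any procedure related adverse events". Then: "These subjects will not count towards the enrollment ceiling and will not be considered for the primary endpoints analysis".
- **Attempt.** Eligible, with any investigational device in the body but no energy delivered to the veins. Followed to 30 days, then withdrawn, and likewise kept out of the primary endpoints.
- **Treated.** "Any screened subject who completes the ablation procedure to the point" of device introduction and cryo-energy delivery. No eligibility condition is attached.

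Section 3.3 assesses primary safety in enrolled subjects who go "to the point that the Cryoablation Balloon is inserted into the subject (Attempt and Treated subjects"). Section 1.2 lists other parts of the system besides the balloon, among them the "Steerable Sheath, 12 F" and the Circular Mapping Catheter.

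Three other places set a wider population. Section 3.1.1 bases the overall endpoint analysis on all Enrolled subjects (everyone who signed consent), Section 3.1.3 repeats this as a control of bias, and Section 3.2 calls the endpoint analysis intent-to-treat.

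Section 1.4.1 defines the endpoint as freedom from device- or procedure-related serious events at 12 months. Its list includes cardiac perforation or tamponade, systemic embolism and air embolism.

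**The concern.** A safety denominator should follow exposure: whoever undergoes the invasive step can have the complication. Here membership depends partly on eligibility, which may be decided after exposure, and partly on whether one particular component was inserted. Perforation, tamponade or embolism can arise at trans-septal access, before the balloon enters. The plan foresees that situation, records the event, and then keeps it out of the rate that is meant to capture procedure-related harm.

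The classes also overlap, and no rule says which one prevails. In an open-label single-arm study, a subject's membership could then be settled after the outcome is known. The resulting rate is to be compared with literature rates (Section 3.3), and early cohorts are analysed for CE Mark and PMDA purposes (Section 3.1.1).

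**Working it through.** **1. No plan figure to reproduce.** Section 3.1.2 is redacted, and Section 3.3 gives no expected MAE rate or threshold. The check is a comparison of definitions, followed by an illustration.

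**2. Who is in the primary safety rate?**

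| Subject | Section 2 | Section 3.3 | Sections 3.1.1, 3.1.3, 3.2 |
|---|---|---|---|
| Ineligible, puncture completed, no balloon | Out | Out (no balloon) | In |
| Ineligible, balloon inserted, no energy | Out (Attempt requires eligibility) | Unclear: balloon condition met, but not an Attempt subject | In |
| Ineligible, cryo-energy delivered | Both Consent Ineligible (out) and Treated | In, as Treated | In |
| Eligible, only the sheath inserted | Attempt: out | Unclear: an Attempt subject, but balloon condition not met | In |
| Eligible, balloon inserted, no energy | Attempt: out | In | In |

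Every row contains a conflict. The fourth row takes the sheath, which Section 1.2 lists as part of the system, to be an investigational device. In the first row Sections 2 and 3.3 agree on exclusion, and this is the group with a completed puncture. In the last row Section 2 and Section 3.3 contradict each other directly.

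**3. What an omitted event does to the rate.** Section 3.3 specifies events divided by subjects with an exact binomial interval. For x events in n subjects the limits are the 0.025 quantile of Beta(x, n − x + 1) and the 0.975 quantile of Beta(x + 1, n − x). From the document, n = 100 is the enrolment target in Section 1.1. Excluded subjects do not count towards the ceiling, so they are added to 100. All event counts, and the numbers of excluded subjects, are assumptions.

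- Excluded subject left out: 2/100 = 2.0% (0.24 to 7.04).
- One excluded subject, with an MAE, added: 3/101 = 2.97% (0.62 to 8.44), a rise of about 1 percentage point.

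**4. Direction.** Adding k subjects with e events raises the rate only if e/k exceeds x/n. From a base of 3/100 = 3.0% (0.62 to 8.52), adding five subjects gives:

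- no event: 3/105 = 2.86% (0.59 to 8.12), slightly lower;
- one event: 4/105 = 3.81% (1.05 to 9.47);
- two events: 5/105 = 4.76% (1.56 to 10.76).

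**5. Smaller cohort.** In the first-30 sub-analysis, suppose one of the 30 is excluded and had the only MAE. The rate is then 0/29 (upper limit 11.94%) instead of 1/30 = 3.33% (0.08 to 17.22).

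**6. Follow-up.** Ineligible subjects with a puncture are followed to discharge and Attempt subjects to 30 days, while the endpoint is at 12 months. A binomial rate has no censoring. Simply adding these subjects to the 12-month denominator would treat them as event-free after their follow-up ends, which can itself lower the rate.

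**The case against.** The strongest reply is that nothing is hidden. A reader might infer that these complications go uncounted altogether, and the SAP does not support that. Section 2 requires them to be recorded. Section 1.4.4 makes all procedure- and device-related adverse events a secondary endpoint, assessed in all available subjects (Section 3.6). Section 3.3 also summarises and lists every adverse event by relationship and timing. This stands: the gap is in the primary MAE rate only.

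A reader might also infer that the exclusion necessarily biases the rate downward. That is not shown either. As step 4 illustrates, the direction depends on the events in the excluded subjects, which are not known.

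It can further be said that an ineligible subject who received cryo-energy is not clearly removed, since Section 3.3 admits Treated subjects, and that the analysis is descriptive with no visible success threshold. Both are right. The first makes that case an ambiguity rather than an exclusion, and the second limits the stakes.

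What remains is that a listing does not correct the headline rate and interval that are set against the literature. The wider populations in Sections 3.1.1, 3.1.3 and 3.2 do not rescue the plan, because they contradict Sections 2 and 3.3 without overriding them.

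**Conclusion.** The point holds for the primary endpoint. The SAP gives incompatible primary safety populations. Followed as written, Sections 2 and 3.3 leave procedure-related MAEs out of the primary rate in subjects found ineligible after a completed puncture, and in Attempt subjects with only the sheath inserted. This is at odds with the scope of the endpoint in Section 1.4.1.

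The primary rate can be understated as a result. With about 100 subjects, each omitted event is worth roughly 1 percentage point. That size rests on assumed counts: the SAP does not say how many subjects would be affected, so the actual effect is unknown and may be nil. The definitions should be corrected before analysis, but the point does not invalidate the study.

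**What to change.** - Define one primary safety population by exposure: every consented subject who had a trans-septal puncture or in whom any study system component was inserted, regardless of eligibility.
- State a precedence for overlapping classes: Treated over Attempt, Attempt over Consent Ineligible.
- Reconcile Sections 2, 3.1.1, 3.1.3, 3.2 and 3.3 with that definition.
- Do not count subjects with short follow-up as event-free to 12 months. Include them in a procedural and 1-month MAE rate, noting which were observed only to discharge. For the 12-month rate, either use a time-to-event estimate that censors at last follow-up, or keep the binomial rate and report these subjects' events beside it with their own denominator.

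The cost is SAP wording and a little extra analysis. For subjects with a completed puncture the events are already recorded to discharge, and for Attempt subjects to 30 days. For an ineligible subject with a component inserted but no completed puncture, the SAP states no follow-up, so what data exist must be checked. The safety rate may become slightly less favourable.
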